Design and Setting. Utilizing clinical lab methods, this aim provides broad testing of the top 4 HWLs on a myriad of WP smokers' subjective and objective outcomes. *We will recruit 2 groups of WP smokers (124 each, total 248; age 18-29 yrs) based on their use frequency (beginners: started WP smoking in the past 6 months, but smoke WP less than weekly; established: smoked at least once a week in the past 6 months) for a 2x2x2x4 within-subject (2: HWL vs no-HWL x 2: pre- vs post- smoking) and between-subject (2: beginner vs established smokers x 4: HWLs) experimental study. Participant in each group (beginner, established smoker) will be randomly assigned to one of the 4 HWLs conditions, and undergo 2 WP smoking sessions that differ by HWL on the WP device (HWL vs. no-HWL), with pre-/post-smoking assessment of harm perception, intention to quit, puffing behavior, satisfaction, urge to smoke, and toxicant exposure (CO, nicotine, oxidative stress) (Figure 9). We will use Latin Square crossover design balanced for carry-over effect (random order of 4 HWL condition), and to ensure equal distribution of study participants across gender. Accordingly, every subject will undergo 2 WP smoking sessions in the clinical lab setting differing by label (HWL vs. no-HWL) in a balanced random sequence; the same number of subjects gets each label and its order (1st or 2nd session) the same number of times, and for each gender. As in (Evans 2015, Brewer 2016, Brewer 2019), all participants will receive a follow-up phone call assessment after 3 months of the last session to evaluate the longer-term effect of exposure to the HWLs in real-world setting including HWLs recall, social interactions about WP harms (talk about HWLs with family/friends), and behavioral adaptations in response to exposure to HWLs (e.g., harm perception, quit intention, quitting).*

Such an approach allows:

- 1- Thorough comparisons without the need for large samples using powerful within-between subjects design.
- 2- Comparative testing for HWLs with current practice (no label control).
- 3- Comparative assessment of the 4 HWLs, and the themes they represent, on important

outcomes through between-subjects pre-post analysis.

4- Assessment of the expected effect of HWLs on WP smokers at different stages of their smoking trajectory.

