to-medium effect size (Cohen's $f=0.19$) depending on HWL condition ([name] 2019, b). *This study will include 248 WP smokers (124 beginners; 124 established) randomized to 4 groups (62 each) along the 4 tested HWLs. Using repeated measures ANOVA F test with 2 within and 2 between factors, a total sample size of 240 participants will have at least 80% power to detect small-to-medium size effect (Cohen's $f=0.2$) or larger for $2 \times 2 \times 2 \times 4$ within-subject (H WL condition and time) and between-subject (smoking frequency and 4 different HWLs) effects, as well as their interactions at 0.05 level of significance, assuming sphericity and a moderate correlation (0.5) among repeated measures (Cohen 1988). The proposed sample size will provide sufficient power to detect small to medium effects expected based on our pilot data ([name] 2019, b). It is also feasible as we have not encountered any difficulty in recruiting a large number of WP smokers in our lab studies ([name] 2019, a).*

Screening, Informed Consent. Individuals who are identified as potentially eligible based on the phone screening will be asked to attend an onsite-screening, which will involve assessment of inclusion/exclusion criteria, physical examination, and urine pregnancy testing for women. Prior to screening, potential participants will undergo a review of the study and consent procedures to ensure that they understand the study, its risks/benefits, and their rights as research participants. Consented (written) individuals will then undergo a physical examination conducted by the research nurse, who will have access to an on-call Medical Monitor (physician) in case of concern or for consultation at any point of the study as it is the standard practice in our lab ([name] 2019, a, [name] 2019, b). The physical examination will include measuring BP, heart rate, temperature, pulse oximetry, and weight/height. Successfully consented/screened participants will be scheduled for their 1st session and asked to abstain from all tobacco use 12 hours prior to it.

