Statistical Analysis. Prior to analysis, physiological data will be averaged to produce a single baseline value for each measure (10 minutes prior to WP use) and for each 10- minute that a participant was actually using the WP. Topography data will be processed automatically by the topography instrument software to eliminate closely spaced puffs (i.e., IPIs < 300 msec). Such puffs are assumed to be part of the previous puff and the recorded volume and duration values will be added to that preceding puff ([name] 2009). After this procedure, any puffs less than 5 ml will be considered an artifact and automatically discarded. Remaining data will be averaged for each participant in each condition using all remaining values for puff volume, duration, number, and IPI (Shihadeh 2004). We will address the issue of stability of WP puff topography by correlating topography values across sessions (Shihadeh 2005a). For plasma nicotine, values below the limit of quantitation (LOQ) will be replaced with the value of the LOQ ([name] 2011). Demographical data will be examined to determine if there are significant between-group differences on measures that may be related to study outcome (some differences are expected due to design such as past 30-day WP use) though these are expected to be minimized as a virtue of randomization. Unexpected between-group differences will be considered as potential adjustment covariates in the primary analysis (Evans 2006). *The primary analysis of each outcome will involve a 4-factor analysis of variance (or covariance) with two within-subject factors; HWL (HWL vs. no-HWL/control) and time (pre-post smoking), and two between-subject factors; smoking frequency (beginner vs. established WP smokers) and HWL (4 group assignment). This approach will be extended into mixed-effects linear regression model in order to adjust for potential confounders such as gender, education, race, SES, and self-efficacy. To assess if gender has any effect on the results, it will be considered as a covariate and we will test the pre-planned interaction with it to determine heterogeneity of HWL by gender as well as potential differential effects.* We will test for carry over effect statistically and will control for it when testing for the primary factors (Senn 2002). Significance levels will be adjusted for violations of the sphericity assumption using Huynh-Feldt corrections (Keppel 1991). The mean square error terms for the overall interaction will be used to conduct Tukey's honestly significant difference test (Keppel 1991), with comparisons at $P < 0.05$ considered significant.

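### The primary model lets a baseline significance screen choose demographic covariates, uses pre-smoking values only as responses, and has no session-order term, so the comparison of the four labels is less precise than it could be.

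*Combined protocol and SAP*

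**What the plan says.** All references are to section C.5 (Aim 2) of the combined protocol and SAP.

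- **Screen.** Statistical Analysis: "Demographical data will be examined to determine if there are significant between-group differences on measures that may be related to study outcome". It then states: "Unexpected between-group differences will be considered as potential adjustment covariates in the primary analysis".
- **Primary model.** Each outcome gets a 4-factor analysis of variance or covariance. The within-subject factors are label condition (HWL, the health warning label, or none) and time (pre or post smoking). The between-subject factors are smoking frequency and label group. No covariate list is fixed for this model.
- **Extension.** A mixed-effects regression adjusts for potential confounders such as gender, education, race, SES and self-efficacy. Gender is to be considered as a covariate, with a pre-planned interaction. Carry-over is to be tested and controlled. No period or session-order term is named.
- **Design.** Under Design and Setting, "the same number of subjects gets each label and its order (1st or 2nd session) the same number of times, and for each gender". The four labels are to be compared on important "outcomes through between-subjects pre-post analysis".
- **Order.** Experimental Methods expects a smaller difference between sessions when the HWL session comes first.

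**The concern.** Labels are assigned at random, so a significant demographic difference between label groups is a chance finding. How large that imbalance happens to be says nothing about whether the variable predicts the outcome, yet it may decide whether the primary model has covariates, and which.

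The second weakness is independent of the first. Pre-smoking values are collected for many outcomes, and session order and gender are balanced in the assignment. All of this is known in advance. The 4-factor model uses the pre-smoking value only as one level of the time factor, leaves session order out, and leaves gender to a possible covariate and the extension model. Comparing the labels is a stated purpose with 62 people per label, so precision that costs nothing to recover matters there.

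**Working it through.** **Inputs.** Sample Size gives 248 participants (62 per label), a power statement for 240, f = 0.2 and alpha 0.05, "assuming sphericity and a moderate correlation (0.5) among repeated measures". The documents give no SD and no expected difference between labels. The f = 0.2 used below for label comparisons, in SDs of a single score, is therefore an assumption.

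**1. The plan's own power figure.** For between-subject effects in repeated-measures ANOVA, λ = f²·N·m / [1 + (m−1)ρ], with m = 4 measurements. At N = 240, λ = 0.04 × 240 × 4 / 2.5 = 15.36. The least powerful test (8 cells; 7 and 232 df) has 81.8% power, which agrees with the stated 80% or more. The sample size reproduces.

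**2. Variance of a label contrast in the HWL session**, in units of σ², with equal pre and post variance:

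- post value alone: 1
- change score: 2(1−ρ)
- post value adjusted for pre value: 1−ρ²

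| ρ | Change | Adjusted | Reduction |
|---|---|---|---|
| 0.3 | 1.40 | 0.91 | 35% |
| 0.5 | 1.00 | 0.75 | 25% |
| 0.7 | 0.60 | 0.51 | 15% |

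At ρ = 0.5 the change score has the same variance as the post value alone. Adjustment multiplies the standard error by √0.75 = 0.87, so 180 participants would do the work of 240.

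**3. Omnibus power for four labels**, N = 248, λ = 0.04 × 248 / variance, 3 and 240 df:

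| ρ | λ change | Power | λ adjusted | Power |
|---|---|---|---|---|
| 0.3 | 7.09 | 59% | 10.90 | 79% |
| 0.5 | 9.92 | 75% | 13.23 | 87% |
| 0.7 | 16.53 | 94% | 19.45 | 97% |

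For the HWL-minus-control contrast between labels, the difference of changes has variance 4(1−ρ) = 2.00 at ρ = 0.5. The post-smoking difference adjusted for the pre-smoking difference has 2(1−ρ) = 1.00. Power goes from 43% to 75% under the same assumed f.

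**4. Session order.** Let a shift of δ SD affect only the post-smoking value in one session. With balanced order and no order term, it adds δ² to the variance of the HWL versus no-HWL contrast. The plan's HWL-by-time contrast has variance 2 at ρ = 0.5, so its standard error is inflated by √(1 + δ²/2): √1.045 = 1.02 at δ = 0.3 and √1.125 = 1.06 at δ = 0.5. For a post-only difference (variance 1), the factors are √1.09 = 1.04 and √1.25 = 1.12. A shift common to pre and post cancels in the HWL-by-time contrast. The values of δ are assumptions.

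**5. Chance flags.** If 5 to 10 independent variables are tested at 0.05, at least one is flagged by chance with probability 1 − 0.95⁵ = 23% to 1 − 0.95¹⁰ = 40%. The documents do not give the number tested.

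**6. Where the gain in steps 2 and 3 applies.** The Duke Sensory Questionnaire and the Waterpipe Evaluation Scale are asked only after smoking, and puff topography is recorded only during it, so none has a pre-smoking value. Pre-session exhaled CO must be below 5 ppm. If its SD were one tenth of the post-smoking SD with ρ = 0.3, the variance would fall only from 1 + 0.01 − 0.06 = 0.95 to 0.91, about 4%. Plasma nicotine is measured after 12 hours of abstinence meant to clear it. The gain is relevant to harm perception, quit intention, smoking urges and withdrawal, and possibly to the breath-condensate markers.

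**The case against.** A reader might infer that covariates enter only through the screen and that baseline information is thrown away. The text does not support that. Smoking frequency is always a model factor, the extension names its covariates without a test, gender has a pre-planned interaction, and pre-smoking values are in the model through the time factor. The precision loss is relative to covariance adjustment.

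A reader might also attribute the 75% versus 87% contrast to the screening sentence. That sentence concerns demographic data and does not govern pre-smoking values. The contrast is between change-score analysis and covariance adjustment, under an assumed effect. On the plan's own formulation, the label main effect has 91.9% power at N = 240.

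Nor is every flagged difference a chance one. The section's example of an expected difference, past 30-day use, can only concern beginners versus established smokers, who are not randomised. Unexpected differences there may be real confounding of the second hypothesis, so deleting the screen without a replacement would leave that comparison worse specified.

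Finally, no inflation of the type I error has been shown.

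These points narrow the concern but do not remove it. For the label groups the screen still selects on chance, no pre-smoking covariate or order term is named, and the section does not say clearly whether the ANOVA or the adjusted mixed model is primary.

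**Conclusion.** The point holds as two related weaknesses in one section: a significance screen that is a poor way to choose covariates for randomised groups, and a primary model that does not use pre-smoking values as covariates or include session order. It is not a sample-size error.

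The main cost is precision in the label comparisons: 15% to 35% avoidable variance in the HWL session for correlations of 0.7 to 0.3, and 25% at the plan's 0.5. This rests on equal pre and post variances; the power figures also rest on the assumed f = 0.2. It is limited to outcomes with an informative pre-smoking value. The cost of omitting session order is smaller, about 2% to 6% on the standard error of the HWL-by-time contrast for an assumed shift of 0.3 to 0.5 SD. The change is worth making because it is nearly free.

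**What to change.** - Drop the significance screen as a route to covariates for the label comparison.
- Prespecify session order and gender in the primary model of every outcome, alongside frequency group, which is already there.
- For between-label comparisons, analyse the post-smoking value adjusted for the pre-smoking value where one exists. Use the session-1 value for a comparison within the HWL session, and the pre-smoking difference between sessions for the HWL-minus-control comparison. For participants who have the HWL session first, the second pre-smoking value follows label exposure, so the plan should say how this covariate is handled if there is carry-over.
- For beginner versus established smokers, fix the confounder list in advance from the covariates the section already names.
- State whether the ANOVA or the adjusted mixed model is primary.

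The cost is a few degrees of freedom and analysis wording. No new data are needed.

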- 2. Test the top 4 HWLs in a clinical lab experiment.** Using the top 4 HWLs on the device, we will recruit 2 groups of WP smokers (n= 248; age 18-29 yrs) based on their use frequency (beginners, established) for a within- (HWL vs no-HWL; pre- vs post- smoking) and between-subject (beginner vs. established; 4 HWLs) experiment. Participants will be randomly assigned to one of the 4 HWLs conditions and undergo 2 smoking sessions that differ by HWL (HWL vs. no-HWL), with pre-post smoking assessment of harm perception, intention to quit, and toxicant exposure. Participants will receive a follow-up phone call 3-month after exposure to assess longer-term changes in quit attitude and behavior. *We hypothesize that applying pictorial HWLs to the WP device will; 1- significantly increase harm perception and intention to quit, and reduce puffing behavior, satisfaction, and exposure to toxicants compared to no-HWL; 2- this effect will be more pronounced in beginner than established smokers.*
- 3. Disseminate knowledge.** We will partner with *Golin, Tobacco-Free Workgroup, and Truth Initiative* to advocate for the adoption of HWLs policies and disseminate knowledge about WP harmful effects to young people in Florida and nationally.

Impact: Communicating WP risks through HWLs promises to reduce WP use and WP-related morbidity and mortality among young adults in the US.

Research Strategy (68,000 characters) 69,450

A. SIGNIFICANCE

This application is a resubmission. We thank the reviewers for their constructive comments and positive evaluation of our application. It was encouraging that the reviewers identified several strengths and the overall value of our proposal and gave it an “Outstanding” total impact score of “2”. We equally recognize our application shortcomings identified by the reviewers and tried our best to respond to them thoroughly in this resubmission. Our response letter provides a summary of changes made (pls. see response letter), while the revisions introduced in the proposal are marked by italics.

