C.1.2. Experience in using clinical lab methods to provide evidence for WP regulation. Our team has pioneered the use of clinical lab methods to the study of WP, and has applied them recently to the study the potential of tobacco flavor regulation for the WP ([name] 2009, [name] 2019, a). In preparation for this application, [name] and [name] conducted a proof-of-concept pilot study to test the potential effect of HWLs on the device on WP smokers' satisfaction, and exposure to toxins ([name] 2019, b). We recruited 30 WP smokers, who completed two, 45-minute ad libitum smoking sessions that differed by HWL undivided condition (with vs. without) in a crossover design study. Exhaled carbon monoxide (eCO) was measured before and after each smoking session, and participants completed questionnaires assessing their smoking experiences and perceptions. This pilot study showed that placing HWL on the WP device has the potential to reduce WP smoker's positive experiences, and exposures (e.g. eCO). For example, we found lower levels of eCO following smoking the WP fitted with HWL (17.8 ppm) compared with smoking WP without HWL (24.5 ppm; $P<0.05$) (Figure 6). We will build on this experience by conducting a larger, well-powered, theory-driven study with a comprehensive assessment of change in harm perception and intention to quit, dependence, oxidative stress in EBC, and puffing behavior among young WP smokers in Florida.

C.1.3. Experience in using communication approaches to disseminate research results and advocate for policy change. In the past 2 years, [name], [name], and [name] have been collaborating to produce several educational videos about the harmful and addictive profile of WP smoking targeting different audiences (TV Channel 6). These videos have been used by Tobacco Free Florida to increase WP smokers and nonsmokers' awareness about WP health

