[name] has recently received an R01 from NIDA/FDA (R01DA042477) to establish a clinical lab at FIU to study the effect of tobacco flavor manipulation on WP smokers' experiences and behavior, as to guide the FDA of the expected effects of flavor regulation (pls. see FIU Resources) ([name] 2019, a). In this proposal, we will utilize this lab model to study the effect of HWL manipulation on a myriad of WP smokers' subjective (e.g. dependence, harm perception, intention to quit) and objective outcomes (e.g. puffing behavior, exposure to toxicants). The study will compare the main outcomes described below pre- vs post- WP smoking under HWL vs. no HWL conditions. We will use the 4 HWLs that performed best from each theme in Aim 1 to assess the study's outcomes as discussed below.

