Objectives and Hypotheses. To assess WP smokers' responses to the developed pictorial HWLs and inform the state of Florida about HWLs potential to curb WP use among youth in Florida. The study will examine smokers' harm perception, intention to quit, puff topography, satisfaction, dependence, and toxicants exposure (CO, nicotine, EBC oxidative stress) pre-post smoking under 2 conditions (H WL vs. no-H WL). We hypothesize that 1) HWLs on the device will reduce smoking (puffing) intensity, satisfaction, exposure to toxicants, dependence parameters and increase harm perception and intention to quit compared to no-HWL control; and 2) this effect will be more pronounced in beginning vs. established WP smokers.

Participants, Recruitment, and Procedures. As in Aim 1, in this study we will recruit WP smokers through the same online, offline and in-person recruitment methods described in section (C.2.2. Recruitment, Aim 1). Individuals who report smoking cigarettes or other tobacco/nicotine products (e.g., e-cigarettes, pipes, cigars) will be included to increase the generalizability of results, as long as they identify themselves as primarily WP tobacco smokers (do not report using cigarettes/e-cigarettes/other tobacco products regularly > 4 times/month). Concurrent regular use of other tobacco/nicotine products would bias the measurement of WP associated outcomes (e.g. dependence measures) (Ben Taleb 2018). *Participants completing the 2 lab sessions and 3-month follow-up will be compensated \$36 for each visit. Based on previous experience ([name] 2019, a), we expect to study 8-10 subjects/month. We will continue recruitment until we reach the target sample (248 with complete sessions). While recruitment is always a challenge, our lab, led by Co-PI [name] has easily recruited >150 WP users for two-session study (similar design) in the past 2 years with negligible drop out using comparable incentives ([name] 2019, a). This is due to the widespread of WP smoking among college students in Florida (up to 34%) (Martinasek 2016), especially in a large university with about 57,000 students such as FIU, where our lab is located.*

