Inclusion Criteria. Participants need to be generally healthy (at a screening physical examination), between the ages of 21-35 years, willing to provide written informed consent, attend the lab as required, abstain from WP or any tobacco/nicotine for ≥ 12 h prior to study verified by expired air carbon monoxide eCO<5 ppm (Ben Taleb 2018), and use a WP to smoke tobacco in the lab according to study protocol. The 12 hour abstinence period is needed to clear plasma nicotine from prior-to-study smoking (6-8 h after cessation is needed to clear plasma nicotine) (Benowitz 2009) and ensure that all study measures are influenced mainly by study conditions. *Self-reported WP use will be used to define 2 groups of WP smokers (beginners, established), which mostly reflects smokers at different stages of their WP use trajectory ([name] 2016). These are consistent with common WP use patterns among young people in the US, and our previous lab studies with WP smokers, which will enhance recruitment and generalizability of our results (Primack 2013, Haider 2015).*

Exclusion Criteria. As is standard for clinical lab studies involving smoking, safety concerns require that individuals with self-reported history of chronic disease, psychiatric conditions, history of cardiovascular disease, low or high blood pressure (BP) (systolic BP>150 mm Hg, or diastolic BP>100 mm Hg), seizures, or regular use of prescription medications (other than vitamins or birth control) be excluded (Ben Taleb 2018). Women will be excluded if they are breast-feeding or test positive for pregnancy (by urinalysis) at screening. Individuals who fail the eCO test may be rescheduled at another date.

Sample Size. We built our calculation of the sample size for this study on eCO differences in our HWL pilot study (pls. see preliminary studies C.1.2. and Figure 6), which reported a small-

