5. Change in WP smoking will be asked at 3-month assessment using 3 items; “*Since you started the study, 1- did you stop smoking for 1 day or longer because you were trying to quit WP smoking?, 2- did you avoid smoking WP because you were thinking about the HWLs?, and 3- did you stop WP smoking completely because of the HWLs?*” (Brewer 2016).
6. Toxicant exposure includes eCO, plasma nicotine, and EBC oxidative stress.
 - eCo will be measured initially at the beginning of the smoking session (abstinence verification), and within 10 min after the WP smoking session via e-CO monitor (Vitalograph, Lenexa, KS).
 - Plasma nicotine will be assessed pre-/post-smoking. The research nurse will draw Blood samples (~ 10 ml) via a butterfly needle from a forearm vein before smoking session onset and within 10 minutes of its end. Research staff will centrifuge blood samples and freeze plasma immediately, to be analyzed later by Forensic Chemistry Lab at FIU using Liquid Chromatography Mass Spectrometry.
 - Exhaled Breath Condensate (EBC) will be collected pre-post smoking session to test for markers of oxidative stress and DNA damage. We will test for 6 biomarkers (8-oxodGuo, 8-oxoGuo, 8-isoprostanate, formaldehyde, acetaldehyd and malondialdehyde) (Gong 2013, Hu 2015). Samples will be collected during 15 min of tidal breathing through a single-use disposable RTube TM collector (Respiratory Research, Inc., Charlottesville, Va., USA). After sample collection, a plunger will be used to pool the condensed material within the tube into a single sample (about 1.0-2 ml). EBC samples will be divided in aliquots and stored at -80°C. EBC samples will be analyzed by our Forensic Chemistry Lab at FIU using Online Solid-Phase Extraction and Liquid Chromatography Triple Quadrupole Mass Spectrometry (LC-QqQ-MS) and Gas Chromatography Mass Spectrometry (GC-MS) (Hu et al., 2015; Gong et al., 2013). malondialdehyde) (Gong 2013, Hu 2015).

7. Puff topography will be assessed continuously during smoking. It will be measured with a device that was developed by Shihadeh (Shihadeh 2005b), and validated in several WP studies ([name] 2009, Cobb 2015). Briefly, a pressure transducer is integrated into the WP hose, and inhalation-induced pressure changes are amplified, digitized, and sampled at a rate of 1000 Hz. The software converts signals to airflow (ml/sec) and integrates the flow data, producing measures of puff volume, duration, number, and interpuff interval (IPI).

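### The protocol text designates no primary outcome and no model term for the label test, and does not say which domains must be significant to support hypothesis 1

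*Combined protocol and SAP*

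**What the plan says.** In C.5, Statistical Analysis, "The primary analysis of each outcome will involve a 4-factor analysis of variance (or covariance"), with label condition and pre/post time as within-subject factors and smoking frequency and assigned label as between-subject factors. The adjustments named are Huynh-Feldt for sphericity and Tukey's test at P < 0.05.

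On sample size, C.5 says "We built our calculation of the sample size for this study on eCO differences in our HWL pilot study". Power is claimed for the within- and between-subject effects, "as well as their interactions at 0.05 level of significance".

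Hypothesis 1 in C.5, Objectives and Hypotheses, is that "HWLs on the device will reduce smoking (puffing) intensity, satisfaction, exposure to toxicants, dependence parameters and increase harm perception and intention to quit", which makes six domains. The Specific Aims version says labels will "significantly increase harm perception and intention to quit, and reduce puffing behavior, satisfaction, and exposure to toxicants compared to no-HWL". That makes five, because dependence is left out.

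The comparison is described in the opening of C.5: "The study will compare the main outcomes described below pre- vs post- WP smoking under HWL vs. no HWL conditions".

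Under Outcome Measures, "Puff topography will be assessed continuously during smoking", and two questionnaires (DSQ and WES) are given only after smoking. That section also cites Table 1, which was not available to this review.

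**The concern.** The word primary is attached to the analysis of every outcome, so it ranks none of them. Tukey and Huynh-Feldt act within one outcome and do nothing across outcomes. Nothing says whether one, several or all domains must be significant for hypothesis 1 to be supported.

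Nor is it stated whether the label test is the label main effect or the label-by-time interaction. One term cannot serve all outcomes: puff topography, DSQ and WES have no pre-smoking value, so they have no label-by-time term and the promised four-factor model cannot be fitted to them.

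The results are aimed at policymakers and regulators (C.6). With outcomes unranked, a chance favourable result on any one could be reported as a label effect, and readers could not tell it from the result that the study was sized to decide.

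**Working it through.** **The plan's own power figure.** The plan claims at least 80% power with N = 240, f = 0.2 and correlation 0.5. Take the most demanding between-subject effect (8 cells, 7 df) with 4 measurements per person. The noncentrality is 0.2² × 240 × 4 / (1 + 3 × 0.5) = 15.36, and F(7, 232) gives 81.8%. The stated figure is reproduced under this convention; the documents do not say which convention was used.

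**Outcome count (Outcome Measures, C.5).**
- With pre and post values: harm perception 1, intention 1 (three items taken as one), eCO 1, plasma nicotine 1, breath-condensate (EBC) markers 6, QSU 1, MNWS 1; total 12.
- Without a pre value: topography 4, DSQ 1, WES 1; total 6.
- Sum 18, or 20 if the intention items are tested separately. This is our count, not the documents'. It leaves out subscales, cardiovascular measures and 3-month items.

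**False favourable results.** Assume no true effect, one two-sided 0.05 label test per outcome, and that any one significant favourable result counts. A single test has 2.5%. With independence:
- five domains: 1 − 0.975⁵ = 11.9%
- six domains: 1 − 0.975⁶ = 14.1%
- eighteen outcomes: 1 − 0.975¹⁸ = 36.6%

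Outcomes from the same person and session are correlated, but the documents give no correlations. With equally correlated normal test statistics (numerical integration):

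| Assumed correlation | 6 tests | 18 tests |
|---|---|---|
| 0 | 14% | 37% |
| 0.3 | 12% | 26% |
| 0.5 | 10% | 20% |
| 0.7 | 8% | 14% |

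Counting either direction (5% for a single test), the range from correlation 0 to 0.7 is 26% to 16% for six tests and 60% to 28% for 18. If every domain must be significant, the joint error cannot exceed that of a single test.

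**How to read f = 0.19.** In the pilot of 30, "we found lower levels of eCO following smoking the WP fitted with HWL (17.8 ppm) compared with smoking WP without HWL" (24.5 ppm), with P < 0.05. If f is defined before a correlation of 0.5, F(1, 29) = 0.19² × 30 × 2 / 0.5 = 4.33 and P = 0.046, which agrees. If f is scaled by within-subject error, F = 0.19² × 30 = 1.08 and P = 0.31, which does not. The first reading is used below.

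**Power of the label term, N = 248, F(1, 240).** A label effect of 2 × 0.19 = 0.38 SD is assumed after smoking and none before, with equal variances and all correlations 0.5.
- Post-smoking values only: noncentrality 248 × 0.38² = 35.8. Power exceeds 99% at 0.05, 0.05/6 and 0.05/7. The smallest f detectable with 80% power is 0.089 at 0.05 and 0.113 at 0.05/7.
- Main effect in the 2×2 within-subject model: effect 0.38/2, contrast variance 0.5, noncentrality 248 × 0.19² / 0.5 = 17.9.
- Label-by-time: effect 0.38, variance 2, noncentrality 248 × 0.38² / 2 = 17.9.
- For either 2×2 term, power is 98.8% at 0.05, 94.1% at 0.05/6 and 93.4% at 0.05/7. The smallest detectable f is 0.126 at 0.05 and 0.160 at 0.05/7.

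**Power for hypothesis 2.** Assume the beginner–established difference in label effect equals the pooled effect (0.38 SD), with 124 per group.
- Post-only: noncentrality 0.38² × 124 / 2 = 8.95. Power is 85% at 0.05 and 63% at 0.05/6.
- Label-by-frequency-by-time: the variance doubles, so noncentrality is 4.48. Power is 56% at 0.05 and 30% at 0.05/6 (Holm's first step with six tests).

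**The case against.** Several counter-arguments have force.

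- Primary may mean only the main model as against its mixed-model extension. That is plausible, but it still leaves the outcomes unranked. The abstracts and aims repeatedly put harm perception, intention to quit and toxicant exposure first; that is an order of mention, not a designation.
- A reader might infer that no label comparison is specified at all. The documents do not support that. Label versus no-label, pre versus post, is stated. For outcomes measured twice it reads most naturally as label-by-time, and topography is to be averaged within each condition. What is missing is the formal designation of the term.
- Hypothesis 1 joins its domains with an and. Read as requiring all of them, it inflates nothing. The plan does not say that this is the rule, nor that any one result suffices, so the percentages above are conditional.
- A reader might take 60% as the error rate. That figure needs 18 independent outcomes and counts results in either direction; independence is the extreme case.
- Table 1 might contain a ranking. This cannot be excluded, though no visible text refers to one.
- B.2 presents laboratory methods as a first test before real-life implementation, which suggests exploration. However, the Specific Aims predict significant effects and C.1.2 calls the study well-powered.

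**Conclusion.** The concern holds, subject to Table 1. No outcome is designated primary, the term testing the stated label comparison is not designated, and the four-factor model cannot apply to six of the counted outcomes. No rule says what supports hypothesis 1.

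If one favourable result is enough, the chance of a false one rises from 2.5% to between 8% and 14% over six domains, and to between 14% and 37% over about 18 outcomes. These ranges rest on assumed correlations of 0.7 down to 0 and on our outcome count. If all domains are required, there is no inflation.

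This is not a finding that the sample size is wrong. The stated power can be reproduced, and the pooled label test stays well powered under the assumptions shown.

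**What to change.** Before analysis, amend C.5, Statistical Analysis:

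1. Name one primary outcome and one label term (label-by-time or label main effect, if the outcome has pre and post values), tested at 0.05. eCO is the natural default because the sample size rests on it; the investigators may choose another.
2. State that outcomes without a pre-smoking value are tested by the label main effect in a model without time.
3. State which domains must be significant to claim hypothesis 1, or limit the conclusion to the outcomes that pass. Reconcile the five- and six-domain versions.
4. Label all other outcomes, the four-label comparison and the gender interaction as secondary or exploratory. A Holm-adjusted secondary family with one pre-named measure per domain is a reasonable option; any planned test left outside it should be labelled exploratory. Individual EBC markers would be reported as exploratory.

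N and the primary 0.05 do not change. Individual EBC markers, presented in B.2 as an innovation, lose confirmatory status. The real cost falls on hypothesis 2 if it joins the Holm family, as the power losses above show. The investigators may therefore keep it as a separate pre-named test on the primary outcome. Effect sizes for the other secondary outcomes are not given, so their loss of power cannot be calculated.
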